11.3 Documenting and Reporting of Adverse Events by Investigator

Ocular or neurologic adverse events of any grade related to cytarabine and other grade 3-5 non-hematologic and hematologic toxicities and associated toxicities, such as bleeding and infection must be fully recorded in the subject's case record form.

Revise documentation and recording requirements as required.

A laboratory test abnormality considered clinically relevant, e.g., causing the subject to withdraw from the study, requiring treatment or causing apparent clinical manifestations, or judged relevant by the investigator, should be reported as an adverse event. Each event should be described in detail along with start and stop dates, severity, relationship to cytarabine, action taken and outcome.

Every attempt should be made to describe the adverse event in terms of a diagnosis that encompasses the component signs and symptoms. If only nonspecific signs or symptoms are present, then these should be recorded as separate diagnoses on the pages of the case report form.

All subjects who have adverse events, whether considered associated with the use of study drug or not, must be monitored to determine the outcome. The clinical course of the adverse event will be followed according to accepted standards of medical practice, even after the end of the period of observation, until a satisfactory explanation is found or the Principal Investigator considers it medically justifiable to terminate follow-up. Should the adverse event result in death, a full pathologist's report should be supplied, if possible.

11.3.1 Assessment of Causal Relationship of Study Drug

The Investigator will provide an assessment of the potential causal relationship between adverse events and study medication by determining whether or not there is a reasonable possibility that the event was caused by the study medication. The relationship or association of the adverse event to the study medication will be characterized as not related, unlikely related, possibly related, probably related, or related:

Not Related: There is not a temporal relationship to the study drug administration or the adverse event is clearly due only to the progression of the underlying disease state, intercurrent illness, concomitant medication, concurrent therapy or other known cause.

Unlikely Related: There is little or no chance that the study drug administration caused the adverse event; the event is most likely due to another competing cause, including intercurrent illness, progression or expression of the disease state, or a reaction to a concomitant medication or concurrent therapy appearing to explain the reported adverse event.

Possibly Related: The association of the adverse event with the study drug administration is unknown; however, the adverse event is not reasonably attributed to any other condition.

Probably Related: When a reasonable temporal relationship exists between the adverse event and the study drug administration; significant symptoms abate upon discontinuation of the study drug and there is a reasonable explanation based on known characteristics of the study drug and there is no clear association with preexisting disease or therapy, intercurrent illness, concurrent therapy or other factor(s).

Related: When the adverse event is a known side effect of the study drug or there is a temporal relationship to the administration of the study drug; or the adverse event reappears upon re-administration of the study drug (rechallenge); or the significant symptoms of the adverse event abate upon discontinuation of the study drug (dechallenge).

11.3.2 Intensity of Adverse Events

The intensity of adverse changes in physical signs or symptoms will be graded according to the most up-to-date CTCAE version. For all other adverse events not described in the CTCAE, the intensity will be assessed by the Investigator using the following categories:

Mild (Grade 1) – transient or mild discomfort; no limitation in activity; no medical intervention/therapy required.

Moderate (Grade 2) – mild to moderate limitation in activity, some assistance may be needed; no or minimal medical intervention/therapy required.

Severe (Grade 3) – marked limitation in activity, some assistance usually required; medical intervention/therapy required, hospitalization is possible.

Life-threatening (Grade 4) – extreme limitation in activity, significant assistance required; significant medical intervention/therapy required, hospitalization or hospice care probable.

Death (Grade 5) – the event resulted in death.

11.3.3 Action Taken with Study Drug

The action the Investigator took with study drug as a result of the event should be recorded as one of the following:

None – No action was taken with regard to chemotherapy as a result of the adverse event.

Interrupted – Chemotherapy was stopped due to the adverse event, but was later resumed at the same dose.

Dose decreased – The dose of cytarabine was decreased as a result of the adverse event.

Permanently discontinued – The subject was withdrawn from the study due to the adverse event.

Only one item should be chosen. If multiple actions apply, the following “worst case” scenario hierarchy should be used to determine the preferred entry:

permanently discontinued > dose decreased > interrupted.

11.3.4 Definition of Outcome

The outcome of the AE should be recorded as one of the following:

Resolved without sequelae – The subject fully recovered from the adverse event with no observable residual effects.

Resolved with sequelae – The subject recovered from the adverse event with observable residual effects.

Not resolved – The adverse event was present at the time of last observation.

Death – The subject died as a result of the adverse event.

11.4 Reportable Events

11.4.1 Serious Adverse Events

Serious (requiring hospitalization and/or increased level of care) adverse events (SAE's) that are unexpected (not in informed consent) and most likely related to cytarabine must be reported to the IRB within five working days. If there are more than three grade 3-5 neurologic adverse events, these will be reported to the IRB within 5 working days, and enrollment will be suspended until each case is evaluated for causality. If only limited details are known, these should be reported within that time frame and follow up reports can be submitted for elaboration, clarifications, or corrections. Any email correspondence must be kept in the trial file at the study site. The site investigator is responsible for informing the IRB and/or the Regulatory Authority of the SAE as per local requirements.

Follow-up information will be submitted to the IRB stating that this is a follow-up to a previously reported SAE and giving the date of the original report. Each re-occurrence, complication, or progression of the original event should be reported as a follow-up to that event regardless of when it occurs. The follow-up information should describe whether the event has resolved or continues, if and how it was treated, and whether the participant continued or withdrew from study participation.

12. STATISTICAL METHODS

The sections below provide an overview of the statistical considerations and analyses.

12.1 Data collection and management plan

Data will be collected using a CRF managed by the Oncology Clinical Pharmacy Specialists under the supervision of the PI. Information collected from the CRF will be entered into a secure, encrypted, password protected that only the PI and co-investigators have. Regulatory specialists and managers will be involved with the protocol once IRB application is submitted and while the protocol remains open with the IRB.

12.2 Sample Size Justification

This is a prospective single group study to determine the duration of neutropenia after consolidation chemotherapy with HiDAC 123. A historical control group will be selected by identifying patients who received cytarabine 1000 mg/m² IV q12h D135 from 2/1/2017-

2/1/2019 by propensity matching factors: age (+/- 3 years), gender (male or female), Karnofsky PS (90-100/70-80/50-60), and number of HiDAC cycles. The hypothesis is that patients with HiDAC123 treatment schema have a shorter duration of neutropenia after consolidation chemotherapy, compared to matched historical controls who received HiDAC 135. Group sample sizes of 23 subjects from a prospective cohort and 23 subjects from historical baseline group will achieve 81% statistical power to reject the null hypothesis of equal means when the population mean difference in neutropenia duration is three days (16 vs. 19 days) with a standard deviation for both groups of four days and statistical significance level (alpha) of 0.05 using a one-sided, two sample, equal-variance t-test. Including 20% drop out rate, we will accrue 29 subjects per cohort.

12.3 Analysis of Primary Endpoint

When the required assumptions are met, duration of neutropenia will be analyzed by a one-sided, two sample, equal-variance t-test. If the normal distribution and equal variance are not validated, the corresponding non-parametric method will be used. Primary analysis will be for cycle 1 of consolidation only. Other cycles will be recorded and use descriptive statistics. Further, multivariable linear regression model of the neutropenia in days with group as the primary independent variable of interest will be fitted, while adjusting for some potential confounding variables, including AML type (WHO and FAB), documented infection in consolidation #1 (yes or no), ELN risk category (favorable, intermediate, high) and MRD positivity (yes or no), WBC at diagnosis (<50,000 or \geq 50,000), delay between induction course and consolidation #1 (less than or more than 40 days), allogeneic HCT (yes or no).

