	lab) and based on the ACSS score classify into two groups having ACSS score ≥ 0 or <0). ACSS score will be evaluated for association with certain endpoints (duration of neutropenia, thrombocytopenia, RR and OS). Peripheral blood samples will be collected and analyzed through [name] lab at the University of Florida and NGS results will be used to calculate the ACSS score.
Study Design:	This is a non-randomized, open-label, single group phase II study for the prospective arm. These subjects will be compared to matched historical controls who received Day 135 consolidation for the primary and secondary objectives. Historical controls will be matched with prospective subjects for age (+/- 3 years), gender (male or female), Karnofsky PS (90-100/70-80/50-60), and number of HiDAC cycles received.
Accrual Goal:	A total of 29 subjects in HiDAC 123 arm. Data collected from these subjects will be compared to data from 29 matched historical controls who received standard HiDAC 135 consolidation.
Inclusion Criteria:	
Individuals eligible for study participation must meet the following criteria:
 
 A. Both males and females ≥ 61 years of age B. A clinical diagnosis of de novo, non-M3 acute myeloid leukemia (AML) confirmed by greater than 20% blasts in peripheral blood or on diagnostic bone marrow biopsy who have completed intensive induction chemotherapy and are confirmed in complete remission #1 (defined by < 5% myeloblasts on recovery BM biopsy (ANC $> 1000/\mu\text{L}$ and platelets $> 100 \times 10^3/\mu\text{L}$) and able to receive HiDAC consolidation #1. C. Patients on the prospective arm must be willing to have labs/clinic visits at UF Health Shands after discharge from chemotherapy approximately every 48 hours +/- 24 hours until neutrophil and platelet count recovery after each chemotherapy cycle per standard of care to be included. 
 - If prospective subjects cannot be followed at the UF site then telephone visits are allowed to follow for toxicity and transfusions. Records can be requested from subject's local physician office.

	
D. Written informed consent obtained from the subject and the subject agrees to comply with all the study-related procedures as stated above. For subjects on the historical arm, there will be a waiver of informed consent (as these patients may be deceased or not be available for retrospective consent).

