Statistical Considerations:	
Group sample sizes of 23 subjects from a prospective cohort and 23 subjects from historical baseline group will achieve 81% statistical power to reject the null hypothesis of equal means when the population mean difference in neutropenia duration is three days (16 vs 19 days) with a standard deviation for both groups of four days and statistical significance level (alpha) of 0.05 using a one-sided, two sample, equal-variance t-test. Including a 20% drop out rate, we will accrue 29 subjects per cohort.
 
The primary outcome will be analyzed using one-sided t-test with equal variance or the corresponding non-parametric statistical method, depending on the validation of the assumptions.

Estimated Enrollment Period:	36 months
Estimated Study Duration:	60 months

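### The primary test is unadjusted; the planned regression on four unmatched potential confounders is only supplementary, and no rule says which result governs

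*Combined protocol and SAP*

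**What the plan says.** Section 12.3 gives the primary analysis for cycle 1: "duration of neutropenia will be analyzed by a one-sided, two sample, equal-variance t-test". If normality or equal variance fails, the corresponding non-parametric method replaces it. The synopsis (Statistical Considerations) agrees: "The primary outcome will be analyzed using one-sided t-test with equal variance or the corresponding non-parametric statistical method". It does not mention a regression. Section 12.2 sizes the study on the same test.

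The design is non-randomised (3.1), and the controls were treated between 2/1/2017 and 2/1/2019. The synopsis (Study Design) gives the matching: "Historical controls will be matched with prospective subjects for age (+/- 3 years), gender (male or female), Karnofsky PS (90-100/70-80/50-60), and number of HiDAC cycles received". Sections 3.1 and 12.2 list the same four factors.

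Section 12.3 then adds, introduced by the word *Further*, a multivariable linear regression of neutropenia days on group, "while adjusting for some potential confounding variables". The listed variables are AML type, documented infection in consolidation #1, ELN risk category, MRD positivity, WBC at diagnosis, delay from induction to consolidation #1, and allogeneic HCT. No section makes this regression the primary result or says what is concluded if it and the t-test differ.

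**The concern.** Four of the listed variables are fixed before cycle 1 and are not matching factors: ELN risk, MRD, WBC at diagnosis and induction-to-consolidation delay. The plan thinks they may confound the comparison, yet the test it designates as primary omits them. In a randomised trial that would be a matter of efficiency. Here the cohorts come from different periods, so the distribution of these factors may differ systematically, and such a difference passes straight into the estimated schedule effect.

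The synopsis rationale says the team would like to adopt the schedule as standard if the published results are confirmed. With two analyses of one endpoint and no stated precedence, a disagreement between them would be settled after the data are seen.

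**Working it through.** **Inputs from the plan (12.2).** 23 per group, difference 3 days (16 vs 19), SD 4 in both groups, one-sided alpha 0.05, stated power 81%.

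**Reproducing the plan's figure.** The standard error of the difference is 4 × √(2/23) = 1.180 days. The noncentrality is 3 / 1.180 = 2.54 on 44 df, with critical value 1.680. The noncentral t gives power 80.5% and the normal approximation 81.6%, in line with the stated 81%.

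**Bias from an unmatched factor (assumed values).** For a binary factor, bias = (systematic difference in prevalence between cohorts) × (effect of the factor in days). The rejection probability then follows from the noncentral t:
- With no schedule effect and the difference favouring HiDAC 123, noncentrality = bias / 1.180. This gives the one-sided error.
- With a true 3-day effect and the difference running the other way, noncentrality = (3 − bias) / 1.180. This gives the power.

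For a 20-point difference at 23 per group:

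| Factor effect | Bias | One-sided error (favours HiDAC 123) | Power (reverse direction) |
|---|---|---|---|
| none | 0 | 5.0% | 80.5% |
| 1 day | 0.2 day | 7.0% | 76% |
| 2 days | 0.4 day | 9.5% | 70% |
| 3 days | 0.6 day | 12.6% | 64% |

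The error reaches 10% at a bias of about 0.44 day, which is 0.44/4 = 0.11 SD, or 15% of the 3-day target. At a 20-point difference that needs a factor worth about 0.44/0.20 = 2.2 days. At 29 per group the threshold is 0.39 day, or about 1.9 days.

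**Chance versus systematic imbalance.** When a 3-day factor has 40% prevalence in both populations, simulation (23 per group, total SD 4, 40,000 runs) gives an unadjusted error of about 5%, although about 9% of runs show a favourable imbalance of 20 points or more. Inflation therefore needs a real difference between the cohorts.

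**Effect of adjustment.** Simulations with one imbalanced binary factor used effects of 2 to 4 days, differences of 10 to 30 points, and 23 or 29 per group. The unadjusted error was 6.9% to 30.7%. With the factor in the model it was 4.4% to 5.4%.

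**Power cost.** ELN risk (three categories) takes 2 df, and MRD, WBC and delay take 1 each: 5 in all, leaving 44 − 5 = 39. The residual SD is 4 × √(1 − R²), and variance inflation for group is taken as 1.00 to 1.12. The documents give no R², so a range is shown:

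| R² | Power, 23 per group |
|---|---|
| 0 | 76% to 80% |
| 0.13 | 81% to 85% |
| 0.25 | 86% to 89% |

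R² of about 0.13 matches a 3-day factor at 40% prevalence: 9 × 0.24 / 16 = 0.135. If missing covariates cut complete cases to 20 per group, power without variance inflation is about 75% at R² 0 and 80% at R² 0.13.

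**The case against.** The strongest reply is that adjustment is already planned. Under the heading for the primary endpoint, 12.3 prespecifies a regression containing all four variables with group as the variable of interest, and the controls are matched on four other factors. A reader might infer from the t-test alone that the plan ignores confounding. It does not. What stands is narrower: the adjusted result is supplementary and there is no rule for disagreement.

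A reader might also infer that any modest imbalance more than doubles the 5% error. The documents do not support that. They give neither a covariate effect nor an expected imbalance, and 12.3 calls these variables only potential confounders. Chance imbalance is already within the t-test's error. A 20-point systematic difference doubles the error only for a factor worth more than about 2.2 days; the 3-day case assumes a factor as strong as the target effect. The eligibility criteria in 4.2 and 4.3 (de novo, non-M3, first remission with count recovery, no FLT3 or IDH inhibitor) also narrow the room for a shift. These points limit the size but do not remove the concern, because the controls are non-concurrent and these four factors are not matched.

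Two practical objections also stand. Availability in controls is not shown: 2.3.2 records sequencing results only if available, WBC at diagnosis is not itemised in section 6 or 6.1, and exclusion J illustrates inadequate records only with between-cycle data. Durations may also be non-normal, so an adjusted primary analysis needs its own fallback.

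**Conclusion.** The point holds as a matter of which analysis carries the conclusion. Of two analyses already planned, the one less protected against a systematic cohort difference is primary, and precedence is not stated. On the plan's n and SD, with an assumed 20-point difference and a factor worth 1 to 3 days, the one-sided error is 7.0% to 12.6% in one direction and power is about 76% to 64% in the other. These figures show sensitivity; they are not estimates of the bias in this trial. The t-test is valid if the cohorts do not differ systematically on prognostic factors.

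It would also be too strong to say that adjustment makes the comparison unconfounded. The return to about 5% assumes a single measured, correctly modelled factor. Unmeasured calendar-time differences from 2017-2019 would remain. The change is worthwhile because it removes a named, measurable source of bias at small cost.

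**What to change.** In 12.3 and the synopsis:

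- Make the group coefficient from the planned linear model of cycle 1 neutropenia duration the primary analysis, one-sided at 0.05, with a confidence interval.
- Adjust only for covariates fixed before cycle 1: ELN category, MRD, WBC at diagnosis and induction-to-consolidation delay.
- Leave out infection in consolidation #1 and allogeneic HCT, which arise after treatment starts. State why AML type is left out (many levels for this sample size).
- State a rule for missing covariates that keeps all subjects, for example a missing category or multiple imputation.
- Name an adjusted fallback for non-normal durations, for example a rank-based, robust or bootstrap version of the model.
- Report the unadjusted t-test as supportive, and state that the conclusion rests on the adjusted estimate.

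The cost is wording, about 5 degrees of freedom, and a check that the four covariates can be retrieved for controls. If none is prognostic, up to about 4 points of power are lost (80.5% to 76%); dropping incomplete cases would lose more. Section 12.2 can keep its calculation with a note giving this range.
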